9.4.9. Immunogenicity Assessments

As detailed in the Schedule of Activities (Section 2), blood samples for immunogenicity testing will be collected to determine antibody production against LY3303560. Additional samples may be collected if there is a possibility that an AE is immunologically mediated. In case of a hypersensitivity reaction, serum drug concentrations will also be measured to aid interpretation of the immunogenicity data.

Additional samples for immunogenicity testing will be taken approximately every 3 months after the last follow-up visit when:

- 1) Patients have an anti-drug antibody (ADA) titre of 1:5120 or higher at the final follow-up visit. Samples for immunogenicity will be taken approximately every 3 months until the titres drop below 1:5120, for up to a maximum of 1 year after last dose
- 2) Patients have increasing ADA titres at the final follow-up visit compared to previous titres. Samples for immunogenicity will be taken up to a maximum of 1 year after the last dose or until the titres begin to decrease (and also drop below 1:5120, if the titre was 1:5120 or higher at the final follow-up visit)
- 3) Patients had an immunologically mediated AE judged to be potentially associated with ADAs at any time during treatment and have a positive ADA titre at the last follow-up visit. Samples for immunogenicity will be taken up to a maximum of 1 year after the last dose.

Immunogenicity will be assessed by a validated assay designed to detect ADAs in the presence of LY3303560. Antibodies may be further characterised and/or evaluated for their ability to neutralise the activity of LY3303560.

Samples will be retained for a maximum of 15 years after the last patient visit, or for a shorter period if local regulations and Ethical Review Boards (ERBs) allow, at a facility selected by the sponsor. The duration allows the sponsor to respond to future regulatory requests related to LY3303560. Any samples remaining after 15 years will be destroyed.

9.5. Pharmacokinetics

At the visits and times specified in the Schedule of Activities (Section 2), blood samples will be collected to determine the serum concentrations of LY3303560. A maximum of 5 samples may be collected at additional time points during the study if warranted and agreed upon between both the investigator and sponsor. Instructions for the collection and handling of blood samples will be provided by the sponsor. The actual date and time (24-hour clock time) of each sampling will be recorded.

On the day of dosing, PK samples should be collected from the arm that did not receive the IV infusion of study drug.

Drug concentration information that may unblind the study will not be reported to investigative sites or blinded personnel until the study has been unblinded.

9.5.1. Cerebrospinal Fluid Sampling

A lumbar x-ray may be performed at screening to rule out potential contraindications to an LP, such as significant osteoarthritic disease and bone overgrowth. If an x-ray was conducted within 12 months of screening, it may be used.

The LP procedure will be conducted under local anaesthesia by an appropriately qualified person. At each LP, a maximum of 20 mL (including up to 5 mL for local laboratory testing) of CSF will be collected. The first 5 mL of CSF will be collected in a separate container and sent to a local laboratory for testing of white blood cell count, red blood cell count (where possible), total protein, and glucose. In addition, each CSF sample will be visually inspected for evidence of blood contamination. The results of the visual inspection and local laboratory CSF analyses are to be documented on the electronic CRF (eCRF). Grossly evident blood by visual inspection will be reported as positive and documented in the CRF.

Any sample that shows visual or laboratory evidence of blood contamination may be excluded from the PK and statistical analyses if the level of contamination is estimated to be sufficient to produce misleading results.

The remaining CSF will be collected to measure concentrations of CSF biomarkers in all patients and LY3303560 concentrations in patients who are assigned to receive LY3303560. All CSF aliquots remaining after analysis will be stored for exploratory work (Section 9.8).

Patients will be carefully monitored for post-LP headaches. The investigator may use hydration, analgesics, and blood patch to treat any headaches, as clinically indicated.

9.5.2. Bioanalysis

Samples will be analysed at a laboratory approved by the sponsor and stored at a facility designated by the sponsor.

Concentrations of LY3303560 will be assayed using a validated ELISA method. Analyses of samples collected from placebo-treated patients are not planned.

Bioanalytical samples collected to measure IMP concentrations will be retained for a maximum of 1 year following last patient visit for the study.

9.6. Pharmacodynamics

At the visits and times specified in the Schedule of Activities (Section 2), venous blood samples will be collected for measurement of plasma tau concentrations if a suitable assay exists. A maximum of 5 additional time points per patient may be drawn during the study at the discretion of the investigator or sponsor. These additional samples may be drawn to measure LY3303560, tau or exploratory PD biomarker concentrations. Cerebrospinal fluid samples for exploratory PD will be collected as described in Section 9.5.1.

Plasma concentrations of tau and CSF concentrations of tau, p-tau, neurogranin, and A β 1-42 will be determined using validated immunoassay methods. The samples will be stored for a maximum of 15 years after the last patient visit for the study at a facility selected by the sponsor.

Plasma and CSF samples collected for PD measurements will have aliquots stored for future exploratory biomarker work for a maximum of 15 years after last patient visit for the study. Any sample remaining after this period will be destroyed. Research will be limited to investigation of the safety and PD of LY3303560, biomarkers relevant to neurodegenerative diseases, and the mechanism of action of LY3303560. Instructions for the collection and handling of blood samples will be provided by the sponsor. The actual date and time (24-hour clock time) of each sampling will be recorded.

On the day of dosing, for all cohorts, PD samples should be collected from the arm that did not receive the IV infusion of study drug.

9.6.1. *Exploratory Cognitive and Functional Assessments*

The tests of cognitive function (ADAS-Cog₁₄, NTB, MMSE, CDR, ADCS-MCI-ADL24, dCDT, and FCSRT-IR) will be performed during the study at the times specified in the Schedule of Activities (Section 2). These tests are performed as a safety and exploratory measure to document any substantial change associated with treatment, as it is not anticipated that these tests should have significant changes associated with LY3303560 in this small patient population. Cognitive and functional tests may be conducted on separate days within the particular visit's allowed window. However, tests that are performed on the same day should be done in a specific order. Screening tests should be completed in this order: 1) MMSE, 2) FCSRT-IR, 3) CDR, and 4) dCDT. Tests during the study, if done on the same day, should be performed in this order with a minimum of 4 hours separating ADAS-Cog₁₄ and NTB testing to avoid testing fatigue: 1) ADAS-Cog₁₄, 2) ADCS-MCI-ADL24, 3) MMSE, 4) NTB, and 5) dCDT. The study partner (or one of the study partners if there are 2) should be present or available by telephone for the assessment of CDR and ADCS-MCI-ADL (this should be the primary study partner for ADCS-MCI-ADL). When cognitive/functional assessments and LP are scheduled on the same day, all cognitive/functional assessments must be performed before the LP.

9.6.1.1. *Alzheimer's Disease Assessment Scale-Cognitive Subscale*

The ADAS is a rater-administered instrument that was designed to assess the severity of the dysfunction in the cognitive and non-cognitive behaviours characteristic of persons with AD (Rosen et al. 1984); ADAS-Cog refers to the cognitive subscale which was originally designed with 11 items (the ADAS-Cog₁₁). An expanded version that includes 3 additional items more sensitive to patients at earlier stages of AD, the ADAS-Cog₁₄ (Mohs et al. 1997), will be used in this study. It consists of 14 items assessing areas of cognitive function most typically impaired in AD: orientation, verbal memory, language, praxis, delayed free recall, digit cancellation, and maze-completion measures. The ADAS-Cog₁₄ scale ranges from 0 to 90, with higher scores indicating greater disease severity.

9.6.1.2. *Neuropsychological Test Battery*

The NTB is a cognitive tool for clinical trials in the field of AD. The NTB is a collection of several written and oral tests that examines verbal and non-verbal brain functions. The NTB shows linear annual cognitive changes across a wide range of MMSE scores as compared to the

ADAS-Cog₁₄ and is more sensitive than the ADAS-Cog₁₄ among patients with mild impairment (Harrison et al. 2007).

9.6.1.3. Mini-Mental Scale Examination

The MMSE is one of the most widely used screening instruments for cognitive impairment and provides a total score ranging from 0 to 30, with lower scores indicative of greater cognitive impairment (Folstein et al. 1975).

9.6.1.4. Clinical Dementia Rating

The CDR is a clinical staging instrument for dementia (Morris 1993). It characterises 6 domains of cognitive and functional performance: memory, orientation, judgment and problem solving, community affairs, home and hobbies, and personal care. The necessary information to make each rating is obtained through a semistructured interview of the patient and a reliable informant or collateral source (e.g., a family member). The CDR table provides descriptive anchors that guide the clinician in making appropriate ratings based on interview data and clinical judgment.

In addition to ratings on a 5-point scale for each domain (except for personal care, which is rated on a 4-point scale), an overall CDR score is derived by standard algorithm. This score is useful for globally staging the level of impairment: 0 indicates no impairment; 0.5, 1, 2, and 3 indicate very mild, mild, moderate, and severe dementia, respectively.

The CDR and Clinical Dementia Rating-Sum of Boxes (CDR-SB) will be evaluated at screening. The CDR-SB is considered a more detailed quantitative general index than the global score and has reasonable accuracy to discriminate between patients with very early AD and those with MCI.

9.6.1.5. Alzheimer's Disease Cooperative Study/Activities of Daily Living Scale Adapted for MCI Patients

The ADCS-MCI-ADL is a 24-item questionnaire that attempts to detect milder functional impairments and represent a modification of the original activities of daily living scale (Galasko et al. 1997).

9.6.1.6. Free and Cued Selective Reminding Test with Immediate Recall

The FCSRT-IR is a 16-item instrument version of controlled learning (Grober and Buschke 1987) and will be evaluated at screening only. The FCSRT-IR performance as an indicator of early AD comes from correlations with abnormalities in structural and functional imaging and with neurofibrillary lesions in parahippocampal regions that are the earliest targets of AD pathology. Only Form A of the FCSRT-IR will be used in this study.

9.6.1.7. Digital Clock Drawing Test

The Clock Drawing Test (CDT) is used to measure constructional, spatial, and executive abilities, and deficits in the conception of time. On a blank sheet of paper, the patient will be asked to draw a clock showing 10 minutes past 11 (the “command” clock). Next, the patient will be asked to copy a pre-drawn clock showing the same time (the “copy” clock). This test requires different cognitive capabilities in the 2 drawing conditions: the command clock relies more heavily on memory and language; the copy clock relies more on executive function and visual-spatial perception (Rouleau et al. 1996).

The dCDT uses a novel digitising ballpoint pen that functions in the subject's hand as an ordinary ballpoint pen, but digitally records its position on the paper and encrypts the data. Changes in pen position (that cannot be seen by the naked eye) are measured and data are timestamped to enable the system to capture the entire sequence of behaviours, for example, every stroke, pause or hesitation (Souillard-Mandar et al. 2016).

9.7. Genetics

A blood sample will be collected for pharmacogenetic analysis as specified in the Schedule of Activities (Section 2), where local regulations allow.

Samples will not be used to conduct unspecified disease or population genetic research either now or in the future. Samples will be tested for the apolipoprotein E (APOE) genotype ($\epsilon 2$, $\epsilon 3$, $\epsilon 4$) to determine whether these genetic variants are potentially associated with a pharmacological response to LY3303560. Apolipoprotein E genotype has been demonstrated even in small sample sizes to be associated with vasogenic oedema complications. In addition, where local regulations allow, the sample will be stored and analysis may be performed on other genetic variants thought to play a role in response to LY3303560, response to antidementia concomitant therapy, and/or molecular subtypes of AD to test their association with observed clinical outcomes when taking the study drug. While it is unlikely that signals from small trials can be suggested by genetic variance, samples may be saved for analysis particularly for retrospective review if future studies detect associations or other researchers report significant findings. At the current time, possible target genes include, but are not limited to, *Fc γ RII*, *FC γ RIII*, *CLU*, *CR1*, *PICALM*, *MAPT*, *BIN1*, *PSEN1*, and *PSEN2*.

In the event of an unexpected AE or the observation of unusual pharmacological response, the pharmacogenetic samples may be genotyped and analysis may be performed to evaluate a genetic association with response to LY3303560. These investigations may be limited to a focused candidate gene study or, if appropriate, genome wide analysis may be performed to identify regions of the genome associated with the variability observed in drug response. The pharmacogenetic samples will only be used for investigations related to disease and drug or class of drugs under study in the context of this clinical programme. They will not be used for broad exploratory unspecified disease or population genetic analysis.

Other samples may be used for research to develop methods, assays, prognostics and/or companion diagnostics related to disease process, pathways associated with disease state, and/or mechanism of action of the IPs.

All samples will be coded with the patient number. These samples and any data generated can be linked back to the patient only by the investigative site personnel.

Samples will be retained for a maximum of 15 years after the last patient visit, or for a shorter period if local regulations and/or ERBs/IRBs impose shorter time limits, for the study at a facility selected by Lilly or its designee. This retention period enables use of new technologies, response to regulatory questions, and investigation of variable response that may not be observed until later in the development of LY3303560 or after LY3303560 is commercially available.

Molecular technologies are expected to improve during the 15 year storage period and therefore cannot be specifically named. However, existing approaches include whole genome or exome sequencing, genome wide association studies, multiplex assays, and candidate gene studies. Regardless of technology utilised, data generated will be used only for the specific research scope described in this section.

9.8. Biomarkers

Biomarker research is performed to address questions of relevance to drug disposition, target engagement, PDs, mechanism of action, variability of patient response (including safety), and clinical outcome. Sample collection is incorporated into clinical studies to enable examination of these questions through measurement of biomolecules including DNA, RNA, proteins, lipids, and other cellular elements.

Serum, plasma, CSF, and whole blood ribonucleic acid (RNA) samples for non-pharmacogenetic biomarker research will be collected at the times specified in the Schedule of Activities (Section 2) where local regulations allow.

Samples will be used for research on the drug target, disease process, variable response to LY3303560, pathways associated with LY3303560, mechanism of action of LY3303560, and/or research method development, or for validating diagnostic tools or assay(s) related to neurodegenerative diseases.

All samples will be coded with the patient number. These samples and any data generated can be linked back to the patient only by the investigative site personnel.

Samples will be retained for a maximum of 15 years after the last patient visit, or for a shorter period if local regulations and/or ERBs/IRBs impose shorter time limits, at a facility selected by Lilly or its designee. This retention period enables use of new technologies, response to regulatory questions, and investigation of variable response that may not be observed until later in the development of LY3303560 or after LY3303560 is commercially available.

9.9. Health Economics

This section is not applicable for this study.

10. Statistical Considerations and Data Analysis

10.1. Sample Size Determination

A total of 24 patients may be enrolled to ensure 16 complete the study. The sample size is customary for Phase 1 studies evaluating safety, PK and/or PD parameters.

It is expected that at least 4 Japanese patients will be enrolled into the study. Patients will be stratified by Japanese/non-Japanese but not by disease severity at randomisation.

Patients who are randomised but do not complete the study may be replaced to ensure that enough patients complete the study (see Section 5.2).

10.2. Populations for Analyses

10.2.1. Study Participant Disposition

A detailed description of patient disposition will be provided at the end of the study.

All patients who discontinue from the study will be identified, and the extent of their participation in the study will be reported. If known, a reason for their discontinuation will be given.

10.2.2. Study Participant Characteristics

The patient's age, sex, race, weight, height, APOE status, and/or other demographic characteristics will be recorded and may be used in the PK, PD, and safety analyses as quantitative or classification variables. These characteristics will be listed and summarised at baseline, with the exception of weight, which will also be summarised over time.

10.3. Statistical Analyses

Statistical analysis of this study will be the responsibility of Eli Lilly and Company or its designee.

Pharmacokinetic analyses will be conducted on the full analysis set. This set includes all data from all randomised patients receiving at least 1 dose of the IMP according to the treatment the patients actually received. Safety analyses will be conducted for all enrolled patients, whether or not they completed all protocol requirements. Pharmacodynamic analyses will be conducted on all randomised participants who take at least 1 dose of study treatment and have at least 1 postdose PD measurement relevant to the endpoint.

Summary statistics, data tabulations, and data graphs by population (Japanese and non-Japanese, and combined) will be provided as appropriate.

Analyses will be reported by dose. Patients receiving placebo will be pooled into 1 group.

All total and subscale scores will be derived from individual items. If any individual item is missing, the corresponding total and subscale scores will be considered missing, except for the

ADAS-Cog₁₄, which will be imputed. The imputation algorithm will be specified in the statistical analysis plan (SAP).

No formal hypothesis tests are planned. Additional exploratory analyses of the data will be conducted as deemed appropriate.

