5.2. Number of Participants

In each cohort, up to 12 patients may be enrolled so that approximately 8 patients per cohort (6 LY3303560: 2 placebo) provide safety and PK data to steady state.

A maximum of 24 patients will be enrolled.

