## 5. A Priori Statistical Methods

### 5.1. General Considerations

Pharmacokinetic analyses will be conducted on the full analysis set (not including placebo). This set includes all data from all subjects receiving at least one dose of the investigational product.

Safety analyses will be conducted for all enrolled subjects who took study medication, whether or not they completed all protocol requirements.

Additional exploratory analyses of the data will be conducted as deemed appropriate. As this is a Phase 1 study and there will be no formal statistical hypothesis testing, any changes to the planned analysis will not necessitate a protocol amendment and will be detailed in the study report. Summary statistics, data tabulations, and data graphs by ethnicity (Japanese and non-Japanese, and combined) will be provided as appropriate.

Safety reporting will be conducted by Covance; with the exception of QTcF statistical analyses which will be conducted by Eli Lilly. All drug effects, PK, PD, imaging, cognition and exploratory reporting and analyses will be conducted by Eli Lilly.

Where two cohorts are given the same dose and formulation the patients will be pooled together and reported under the same dose levels. Placebo will be pooled across all cohorts.

In recognition that there are now only two dose cohorts in this study, any statistical models detailed in the analysis plan may still be carried out in order to estimate parameters, in particular where changes from baseline are being considered. Without recourse to statistical models, only those patients with both baseline and at least one post-baseline measurement can be included in any summary. Estimates from statistical models may provide additional information, if interpreted appropriately.

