#### 5.1.1. *Handling of Dropouts or Missing Data*

Subjects or patients who discontinue may be replaced at the discretion of the sponsor and investigator. The ethnicity of the replacement subject (Japanese or non-Japanese) should match the ethnicity of the discontinued patient, where possible. Replacement patients will be allocated the same treatment as the dropout patient.

There will be no imputation of missing data.

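### One blank item voids the whole ADCS-MCI-ADL24 total, and the SAP's ban on imputation contradicts even the single exemption, so change scores can be lost from groups of about 4 and 6

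*Protocol*

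**What the plan says.** Protocol 10.3 derives every total and subscale score from its items and adds: "If any individual item is missing, the corresponding total and subscale scores will be considered missing". The one exception is "ADAS-Cog₁₄, which will be imputed", with the algorithm left to the SAP.

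The SAP contains no such algorithm. SAP 5.1.1 states "There will be no imputation of missing data", and SAP 5.7.2, which covers the cognition analyses, has no item-level rule for any scale.

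The strict rule therefore governs:
- ADCS-MCI-ADL24, described in Protocol 9.6.1.5: "The ADCS-MCI-ADL is a 24-item questionnaire that attempts to detect milder functional impairments".
- NTB, described in Protocol 9.6.1.2: "The NTB is a collection of several written and oral tests that examines verbal and non-verbal brain functions". No component list or scoring is given.
- MMSE.

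On who stays in the analysis, SAP 5.1 says that, when no statistical model is used, "only those patients with both baseline and at least one post-baseline measurement can be included in any summary". The MMRM in Protocol 10.3.4.2 and SAP 5.7.2 is optional and takes the pre-infusion score as a covariate.

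On group size, Protocol 5.2 plans that "approximately 8 patients per cohort (6 LY3303560: 2 placebo) provide safety and PK data to steady state", and Protocol 10.3 pools placebo across cohorts.

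**The concern.** A 24-item total has 24 chances of being voided at each visit, and a change score needs two complete totals. A patient with 23 of 24 answers at Visit 2 has no baseline total, so no change from baseline can be formed on that scale. The optional MMRM does not recover this patient, because the missing total is its covariate.

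In groups of about 4 and 6, losing one patient is material. The documents do not say why item imputation suits ADAS-Cog14 but not the longer ADL scale. Protocol 9.6.1 also gives these tests a safety role, to pick up any substantial change, so a change in a patient whose total is voided could go unseen in the summary.

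**Working it through.** **Planned sizes.** Two cohorts of up to 12 give 2 × 12 = 24 enrolled. Two of about 8 give 2 × 8 = 16 completing. Both match Protocol 10.1. Pooled placebo is 2 × 2 = 4, and each dose has 6.

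**Assessments.** As the Schedule of Activities tables read in the extracted text, ADCS-MCI-ADL24 is done at V2, V14 and V20. V14 is the eighth dose, so a 25-week patient has V2 and V20 only, and a 49-week patient has two follow-ups.

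**Assumption.** Each item is missing independently with probability p. The documents give no value, so p runs from 0.1% to 2%.

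**Formulas.**
- One total lost: L = 1 − (1 − p)^24.
- 25-week patient, baseline or the only follow-up lost: 1 − (1 − p)^48.
- 49-week patient, baseline or both follow-ups lost: 1 − (1 − L)(1 − L²).
- At least one of 4 placebo patients lost, if all four follow the 25-week regimen: 1 − (1 − p)^192, since 4 × 48 = 192.

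| p | One total | 25-week change score | 49-week, no change score | At least 1 of 4 placebo (25-week) |
|---|---|---|---|---|
| 0.1% | 2.4% | 4.7% | 2.4% | 17.5% |
| 0.5% | 11.3% | 21.4% | 12.5% | 61.8% |
| 1% | 21.4% | 38.3% | 25.0% | 85.5% |
| 2% | 38.4% | 62.1% | 47.5% | 97.9% |

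Example at p = 1%: 0.99^24 = 0.786, so L = 0.214. For the 25-week patient, 0.99^48 = 0.617, a loss of 0.383. For the 49-week patient, 1 − 0.786 × (1 − 0.046) = 0.250.

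**Precision.** The standard error of a dose-versus-placebo difference is proportional to √(1/n₁ + 1/n₂).
- 4 versus 6: √(1/4 + 1/6) = 0.645.
- 3 versus 5: √(1/3 + 1/5) = 0.730, which is 13% larger.
- 2 versus 4: √(1/2 + 1/4) = 0.866, which is 34% larger.

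**With proration up to 4 missing items.** A total is lost only if 5 or more items are blank, with probability P(Binomial(24, p) > 4). At p = 2% this is just under 0.01% for one total and about 0.02% for baseline plus one follow-up. It is smaller at lower p.

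**NTB.** No item count or scoring is given, so no loss can be computed.

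**The case against.** Several points on the other side are sound.

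- **Low stakes.** The cognition analyses are exploratory and described as underpowered, and no hypothesis test is planned. The primary (TEAE) and secondary (PK) endpoints are untouched. A strict, prespecified complete-item rule is legitimate. This limits the importance of the point but gives no reason to prefer the strict rule.
- **The rates are assumed.** Independence exaggerates the loss, because blank items tend to cluster within an assessment. At 0.1% the loss is under 5%. This stands, and it is why a range is shown.
- **Not every patient has a single follow-up.** A 49-week patient has two, and the lower column applies. If the printed schedule places the first follow-up at V13 rather than V14, the lower column applies to 25-week patients as well.
- **Group sizes are targets.** Up to 12 per cohort may enrol, and Protocol 3.3 already reports 7 active and 2 placebo at 70 mg. The loss percentages do not depend on this.
- **SAP 5.1.1 may mean missed visits, not items.** On that reading the Protocol rule still voids the ADL total, and the SAP still lacks the promised ADAS-Cog14 algorithm.

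A reader might also draw stronger conclusions that the documents do not support.

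- **The lost patients are the more impaired ones, so the arm means are biased.** No pattern of missing items is given. For ADCS-MCI-ADL24 the inference is weak, because Protocol 6.1 and 9.6.1 have the study partner take part.
- **A patient with one blank item contributes nothing.** The rule voids one scale's total and the affected subscale at one visit. Other scales and visits remain.
- **ADAS-Cog14 is safely protected.** It is protected in the Protocol only.

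**Conclusion.** The point holds for ADCS-MCI-ADL24, as a loss of patients and precision on exploratory endpoints. The rule is explicit and nothing in the SAP softens it. A blank item at Visit 2, or at the only follow-up, removes the patient from change from baseline on that scale.

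The size depends on an item-missing rate that the documents do not give. Under independence at 0.1% to 2% per item, the loss is about 5% to 62% for a 25-week patient and about 2% to 48% for a 49-week patient. Clustering would reduce both. No bias in a given direction can be claimed, and nothing can be quantified for NTB.

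Separately, and on the text alone, Protocol 10.3 and SAP 5.1.1 disagree on whether ADAS-Cog14 is imputed.

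**What to change.** Before final unblinding, amend Protocol 10.3 and SAP 5.1.1 and 5.7.2 together. The sponsor's team is unblinded at the dose-escalation reviews (Protocol 10.3.6), so record the date of the change.

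1. **ADCS-MCI-ADL24.** If at most 4 of 24 items are missing, set the total to the sum of the answered items, divided by the maximum attainable on those items, times the maximum total. If more are missing, the total is missing. The limit of 4 is a proposed choice, not a figure from the documents. The item and total maxima must come from the scale's scoring rules, which the documents do not give.
2. **Sensitivity check.** Repeat the summary under the strict all-items rule.
3. **Reporting.** Tabulate the scores lost, by arm and visit.
4. **ADAS-Cog14.** Either write the promised algorithm into the SAP and except it from the ban on imputation, or withdraw the exemption from the Protocol.
5. **NTB.** Define its components and scoring first, then set a comparable rule.

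The cost is a few lines of text and a little programming. The downside is that proration assumes the few unanswered items resemble the answered ones. The strict-rule repeat shows how far the results depend on that choice, but it does not prove the assumption.
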